5.4.3.5 Pharmacokinetic Analysis

Sparse PK analysis may be performed evaluating trough levels for all biologic study intervention and maximum observed drug concentration (Cmax) for exploratory biologic study intervention (non-PD-1 agents). The decision to perform PK analysis will be made on a cohort-by-cohort and compound-by-compound basis.

5.4.3.6 Anti-Drug Antibody Analysis

The number of participants who develop ADA to biologic study intervention and ADA titer may be summarized. The decision to perform ADA analysis will be made on a cohort-by-cohort and compound-by-compound basis.

5.5 Safety Analysis

All safety analyses will be performed on the evaluable population, consisting of all participants who receive at least 1 dose of any component of the combination study intervention. Because this is a non-randomized and open-label study, it is highly unlikely that a participant will receive an incorrect study intervention. Therefore, participants will be grouped according to the cohort into which they were enrolled. If any participants receive incorrect study intervention, it will be recorded as a protocol deviation and described in the Clinical Study Report.

Safety will be assessed through summaries of AEs, laboratory test results (hematology, serum chemistry, and thyroid function testing), vital signs, and ECGs.

5.5.1 Exposure to Study Medication

The number of participants exposed to each study intervention and the extent of exposure (as number of doses and cumulative dose received, as applicable) will be summarized by cohort using descriptive statistics.

5.5.2 Adverse Events

All reported AEs will be coded using the latest version of the Medical Dictionary for Regulatory Activities (MedDRA) and graded using the NCI Common Terminology Criteria for Adverse Events (CTCAE) version 5.0.

A treatment-emergent adverse event (TEAE) is defined as any event that either occurs after the initiation of study intervention, having been absent at baseline, or, if present at baseline, appears to have worsened in severity or frequency, whether or not the event is considered related to study intervention. AEs assessed by the Investigator to be “Possibly”, “Probably”, or “Definitely” related to any study intervention, as well as AEs with missing relationship, will be considered treatment related.

Handling of missing and partial missing AE dates is described in Section 5.6.1.

The incidence of TEAEs will be summarized (overall, by system organ class and preferred term and by severity) by cohort. In addition, separate summaries will be generated for SAEs, deaths, treatment-related AEs, AEs leading to treatment discontinuation, and AEs leading to temporary interruption and/or dose reduction. Participant deaths and the primary cause of death will be listed.

5.5.3 Laboratory Data

Clinical laboratory findings will be summarized using descriptive statistics for each cohort. Changes from baseline to each visit may be presented for select laboratory tests.

5.5.4 Vital Signs

Vital sign measurements will be summarized using descriptive statistics for each cohort. Changes from baseline to each visit may be presented for each cohort.

5.5.5 Physical Examinations

Physical examination data will not be summarized because any significant finding will be captured and summarized as an AE.

5.6 Missing Data

5.6.1 Missing and Partial Missing Adverse Event Dates

If the AE start date is not a complete date, the following rules will be applied to determine whether the event is treatment emergent.

- If the start date is completely missing: The AE will be considered treatment emergent unless the AE stop date is earlier than the date of first dose of study intervention.
- If the day of the AE start date is missing:
 - If the month and year of the start date are later than the month and year of the date of first dose of study intervention, then the AE will be considered treatment emergent.
 - If the month and year of the start date are equal to the month and year of the date of first dose of study intervention and the stop date is unknown or later than the date of first dose of study intervention, then the AE will be considered treatment emergent.
- If the day and month of the start date are missing:
 - If the year of the start date is later than the year of the date of first dose of study intervention, then the AE will be considered treatment emergent.
 - If the year of the start date is equal to the year of the date of first dose of study intervention and the stop date is unknown or later than the date of first dose of study intervention, then the AE will be considered treatment emergent.

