6.1 STUDY INTERVENTION(S) ADMINISTERED

The dose and schedule selected will be described in the cohort appendix for each respective combination (eg, Appendix Cohort A, Appendix Cohort B, etc.). The duration of immunotherapy combination study intervention will be dependent on the combination administered.

Administration of study intervention will be performed in a monitored setting in which there is immediate access to trained personnel and adequate equipment and medicine to manage potentially serious reactions.

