8.3 ADVERSE EVENTS AND SERIOUS ADVERSE EVENTS

The definitions of an AE or SAE can be found in [Appendix 5](#).

Investigators will seek information on AEs at each participant contact until at least 100 days after the last dose of study intervention. AEs reported by the participant (or, when appropriate, by a caregiver, surrogate, or the participant’s legally authorized representative) or noted by study personnel, will be recorded in the participant’s medical record and on the Adverse Event eCRF page. If the AE is determined to meet seriousness criteria, the event will be reported as an SAE on the study-specific SAE Report Form (SAERF) within 24 hours of awareness. Seriousness criteria is defined in [Appendix 5](#).

The Investigator and any qualified designees are responsible for detecting, documenting, and recording events that meet the definition of an AE, AESI (as applicable), or SAE and remain responsible for following up AEs that are serious, considered related to the study intervention or study procedures, or that caused the participant to discontinue the study intervention (see [Appendix 5](#)).

8.3.1 Time Period and Frequency for Collecting AE, SAE, and Other Reportable Safety Event Information

All SAEs will be collected from the time the participant signs informed consent until at least 100 days after the last dose of study intervention. Prior to initiation of study intervention, only SAEs that are-related to a protocol-mandated intervention, including those that occur prior to the assignment of study procedures (eg, screening invasive procedures, such as biopsies) should be reported. After obtaining informed consent, but prior to initiation of study intervention, other medical occurrences will be recorded as medical history.

All AEs, including AESIs (as applicable), will be collected from the start of study intervention until at least 100 days after the last dose of study intervention.

If the Investigator learns of any SAE, including a death, at any time after the end of the AE reporting period, and he/she considers the event to be reasonably related to the study intervention or study participation, the Investigator must promptly notify the Sponsor or its designee. The Investigator should report these events directly to the Sponsor or its designee, either by faxing or emailing the SAERF.

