3.2 Study Objectives and Endpoints

The study objectives and endpoints for the Core Protocol are listed in Table 1. Any cohort-specific endpoints will be captured in an appendix to this SAP.

Table 1: Objectives and Corresponding Endpoints

Objectives	Endpoints
Primary	

 To determine the safety of each immunotherapy combination in participants with mCRPC. 	
 Incidence and severity of AEs.
Secondary	

 To determine the CRR of each immunotherapy combination in participants with measurable mCRPC. 	
 Composite Response Rate (CRR): A composite endpoint where response is defined as a participant meeting at least one of the following:

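### SAP 5.6.1 handles an AE that stops on the day of first dose inconsistently: kept if the start date is wholly missing, not covered if it is only partly missing

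*SAP*

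**What the plan says.** SAP 5.6.1 has a limited scope: "If the AE start date is not a complete date, the following rules will be applied". It then has three branches.

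- **Start date completely missing:** "The AE will be considered treatment emergent unless the AE stop date is earlier than the date of first dose of study intervention".
- **Day missing, month and year equal to those of first dose:** the event counts if "the stop date is unknown or later than the date of first dose of study intervention".
- **Day and month missing, year equal to that of first dose:** the same stop-date condition.

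The section does not say what happens to a record that meets none of the conditions.

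SAP 5.5.2 defines a treatment-emergent AE (TEAE) as "any event that either occurs after the initiation of study intervention, having been absent at baseline", or as one present at baseline that worsens. The primary endpoint in SAP 3.2 is "Incidence and severity of AEs", and SAP 5.5.2 reports it through TEAE tables: "The incidence of TEAEs will be summarized".

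On collection, Protocol 8.3.1 states: "All AEs, including AESIs (as applicable), will be collected from the start of study intervention until at least 100 days after the last dose". Between consent and first dose, only serious events related to a protocol-mandated intervention are reported; other occurrences go to medical history.

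**The concern.** The three branches answer the same question with different amounts of start-date information, so they should agree at the boundary. They do not. The first excludes only stop dates before first dose, so the day of first dose is in. The other two require a stop date after first dose, so the day of first dose is out. Nothing in the SAP explains why knowing the month of onset should make an event less likely to count.

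The boundary day matters because a brief reaction to the first administration can begin and end on it. Protocol 6.1 foresees such reactions when it requires "immediate access to trained personnel and adequate equipment and medicine to manage potentially serious reactions". An event of this kind that began after dosing satisfies the definition in SAP 5.5.2, yet with a partial start date it meets no condition in SAP 5.6.1. Where the event is post-dose, the error can only remove it from the tables, so it runs toward under-reporting.

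**Working it through.** **1. The rule as written.** Let F be the first-dose date and S the AE stop date. For partial dates, the known part of the start date is taken to match F.

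- Completely missing start: treatment emergent unless S < F.
- Day missing, or day and month missing: treatment emergent if S is unknown or S > F.

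Four stop dates against three types of start date give 12 cases:

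| Start date | S unknown | S = F − 1 day | S = F | S = F + 1 day |
|---|---|---|---|---|
| Completely missing | yes | no | **yes** | yes |
| Day missing | yes | no | **no** | yes |
| Day and month missing | yes | no | **no** | yes |

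The branches disagree only in the column S = F.

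**2. The rule with S > F changed to S ≥ F.** The two partial-date cells in the column S = F become yes. The other 10 of 12 cells are unchanged, and events that stopped before first dose remain out.

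**3. Which answer fits the collection rule.** Under Protocol 8.3.1, a non-serious occurrence before first dose is not recorded as an AE. A non-serious AE record with S = F therefore has its onset on the first-dose day, after the start of intervention. A serious record with S = F could instead be a screening-procedure complication that began before dosing. So post-dose onset is the likely reading, but not a certainty.

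**4. Size.** The plan gives no figure for this effect. For scale, the 12 exact 95% intervals in SAP Table 2 were recomputed by the Clopper-Pearson method, and all agree to 0.1 point. One participant is 1/15 = 6.7 points in a Stage 1 cohort and 1/30 = 3.3 points in an expanded one. Examples at n = 15:

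- 2/15 = 13.3% (1.7% to 40.5%) becomes 1/15 = 6.7% (0.2% to 31.9%).
- 1/15 becomes 0/15 = 0%, with upper limit 1 − 0.025^(1/15) = 21.8%.

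These are ceilings for one affected participant. The rate for a preferred term does not move if he has the same term at another time, and the overall TEAE rate does not move if he has any other TEAE. The documents do not say how often a partial start date would occur together with a known stop date on the first-dose day.

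**The case against.** The case on the other side has five parts.

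- **The situation is close to empty.** Reactions at administration occur in a monitored setting, so their start day is unlikely to be missing. Protocol 10.1.8 also provides for quality checks and source data verification, which could complete the date. This stands as to frequency. A reader might infer that same-day reactions in general are lost. The documents do not support that: a complete start date is outside SAP 5.6.1, and a wholly missing one is kept.

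- **Onset before dosing is possible.** A reader might infer that any AE ending on the first-dose day must have begun after dosing. Protocol 8.3.1 and 10.5.1.1 rule that out, because serious events from screening procedures such as biopsies are recorded as AEs. The present wording leaves such an event out correctly, and an on-or-after rule would bring it in. This stands and shapes the fix. It does not justify the strict inequality, since the current rule already counts the same event if it stops one day later.

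- **Exclusion is only implied.** The SAP lists conditions for inclusion and gives no default, so the definition in 5.5.2 might be applied instead. It is true that the exclusion is unstated. But a partial-date event that stopped before first dose is also left out only by silence, so silence is naturally read as exclusion.

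- **The event may be visible elsewhere.** SAP 5.5.2 also calls for summaries of serious and of treatment-related AEs, which are not expressly limited to TEAEs. Under SAP 4.3 the Safety Assessment Committee reviews all AEs. This stands: the possible loss is from the TEAE tables, and safety oversight does not depend on this rule.

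- **A full 6.7 points need not be lost.** A reader might infer that each misclassified participant lowers a rate by that amount. He does so only if he has no other qualifying event in the category.

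**Conclusion.** The point holds as a small internal inconsistency with an unstated default. At the day-of-first-dose boundary, the two partial-date branches of SAP 5.6.1 disagree with the completely-missing branch, and for events that began after dosing they conflict with the definition in SAP 5.5.2. Read as written, the rule can omit a post-dose event from the tables that report the primary endpoint.

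The effect should be rare. Each affected participant changes an AE category by at most one count: up to 6.7 points at n = 15 and 3.3 at n = 30.

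This rests on three assumptions: a record meeting no condition is treated as not treatment emergent; the event began after dosing; and the participant has no other event in the category. The expected effect cannot be estimated from the documents. The matter is one of date classification and bears on no dose, schedule or other clinical management. It is worth correcting because the correction is nearly free.

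**What to change.** Make three changes to SAP 5.6.1.

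1. In both partial-date sub-bullets, let the stop date be unknown, or on or after the first-dose date. This matches the first bullet.
2. State the default for a record that meets no condition.
3. State that a record is not treatment emergent when other recorded information shows that it began before dosing, as with a serious event from a screening procedure, subject to the worsening clause in SAP 5.5.2.

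The third change deals with the one drawback of the first: without it, a pre-dose procedure-related serious event with a partial start date that resolves on the first-dose day would be counted as treatment emergent.

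The cost is an edit to two sentences, two added sentences, a changed comparison in the program and a check for recorded pre-dose onset. No new data are needed.

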5.6.2 Missing and Partial Missing Death Dates

For death dates, the following conventions will be used for imputing partial dates:

- If the date of death is completely or partially missing, but there is an AE with the outcome as 'Fatal', the date of death will be replaced by the end date of the AE.
- If only the day of the month is missing and there is no AE with outcome as 'Fatal', the 1st of the month will be used to replace the missing day. The imputed date will be compared to the last known date alive plus 1 day, and the maximum will be considered as the death date.
- If the month or the year is missing, the death date will be imputed as the last known date alive plus 1 day.
- If the date is completely missing but the reason for death is present, the death date will be imputed as the last known date alive plus 1 day.

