7.2 PARTICIPANT DISCONTINUATION/WITHDRAWAL FROM STUDY

The total length of study participation, from participant screening to the end of study, is expected to be approximately 31 months.

When study intervention is discontinued, participants should have an end of treatment discontinuation assessment followed up by an assessment 14-28 days after the last dose of study intervention as outlined in the SOA (see [Section 1.3](#)). Information on survival follow-up and new anticancer therapy will be collected every 3 months for up to 2.5 years from the initiation of study intervention until any of the following occurs:

- Death
- Loss to follow-up
- Study termination by the Sponsor
- Participant requests to be withdrawn from follow-up

A participant may withdraw consent at any time and discontinue study intervention and further participation in the study. This request must be documented in the source documents and signed by the Investigator. The Sponsor may retain and continue to use any data collected before such withdrawal of consent. Participants who withdraw consent will not be followed for any reason after consent has been withdrawn. However, the study staff may use a public information source (eg, county records) to obtain information about survival status only.

Other reasons for discontinuation of study intervention and/or participation in a follow-up phase of the study may include death, AEs, physician decision, protocol deviation, eligibility not met, progressive disease. A participant is considered to have completed all phases of the study as defined in the cohort appendix for each respective combination, including the lead-in phase, as applicable, the treatment phase, and the safety and survival follow-up after last dose of study intervention.

The primary reason for withdrawal from study should be documented on the appropriate eCRF page.

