- The most appropriate diagnosis or if a diagnosis cannot be established, the abnormal laboratory values should be recorded on the Adverse Event eCRF page and reported to the Sponsor immediately, either as an SAE or an AESI (as applicable and as defined in the cohort appendix for each respective combination).

Lack of Efficacy or Worsening of Underlying Disease

- Events that are clearly consistent with the expected pattern of progression of the underlying disease should not be recorded as AEs. These data will be captured as efficacy assessment data only. In most cases, the expected pattern of progression will be based on the PCWG3-modified RECIST 1.1 used in this study. In rare cases, the determination of clinical progression will be based on symptomatic deterioration. However, every effort should be made to document progression through use of objective criteria. If there is any uncertainty as to whether an event is due to disease progression, it should be reported as an AE.

Deaths

- All deaths that occur during the protocol-specified AE reporting period, regardless of relationship to study intervention, must be recorded on the Death eCRF page and immediately reported to the Sponsor (see [Section 8.3.1](#)), unless the death is attributed to progression of disease.
- Death should be considered an outcome and not a distinct event. The event or condition that caused or contributed to the fatal outcome should be recorded as the single medical concept on the Adverse Event eCRF page. Generally, only one such event should be reported.
- If the cause of death is unknown and cannot be ascertained at the time of reporting, "unexplained death" should be recorded on the Adverse Event eCRF page.
- If the cause of death later becomes available (eg, after autopsy), "unexplained death" should be replaced by the established cause of death.
- The term "sudden death" should not be used unless combined with the presumed cause of death (eg, "sudden cardiac death").

- If the death is attributed to progression of underlying disease, “underlying disease” should be recorded on the appropriate eCRF page; no SAERF is necessary.
- Deaths that occur after the AE reporting period should be reported as described in [Section 8.3.2](#).

Pre-existing Medical Conditions

- A pre-existing medical condition is one that is present at the baseline visit for this study. Such conditions should be recorded on the Medical History eCRF page.

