5.4.2.4 Overall Survival

OS is defined as the time from initiation of study invention until death due to any cause. Participants who are not reported as having died at the time of analysis will be censored at the most recent contact date they were known to be alive. See Section 5.6.2 for handling of missing or partial death dates.

OS will be estimated using Kaplan-Meier techniques, and the median survival time and 95% CIs will be estimated within each cohort. If median survival is not reached, survival times and 95% CIs will be reported at deciles that are estimable given the observed events. In addition, the 12-month OS rate will be estimated within each cohort and 95% CIs will be estimated using the Clopper-Pearson method.

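### When the month of death is missing but the year is known, SAP 5.6.2 ignores the year and can impute a death date that the record excludes (minor)

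*SAP*

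**What the plan says.** SAP 5.6.2 sets out the death-date conventions, and SAP 5.4.2.4 refers to them for OS. Three of the bullets matter here.

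- **Fatal AE present.** If the death date is wholly or partly missing and there is an AE with a fatal outcome, "the date of death will be replaced by the end date of the AE". This comes first.
- **Only the day missing, no fatal AE.** The first of the recorded month is used as a trial value. Then: "The imputed date will be compared to the last known date alive plus 1 day, and the maximum will be considered" as the death date. The recorded month and year are kept.
- **Month or year missing.** "If the month or the year is missing, the death date will be imputed as the last known date alive plus 1 day". There is no comparison with whatever part of the date is known.

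SAP 5.6.1, on AE start dates, does use a recorded year when the day and month are missing. The protocol has no rule for partial death dates, and its section 9.3 lets the SAP prevail where the two differ.

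**The concern.** The third bullet treats two situations alike. If the year is unknown, the day after last known alive is a reasonable earliest date. If the year is known and the month is not, the record already says that death was no earlier than 1 January of that year, and the rule discards this. The bullet just above it keeps the known part of the date by taking a maximum, so the SAP departs from its own logic when one more element is missing.

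The first bullet will not catch every such case. Protocol 10.5.5 says: "Events that are clearly consistent with the expected pattern of progression of the underlying disease should not be recorded as AEs". Many deaths from progression will therefore have no fatal AE. AE collection is required for at least 100 days after the last dose (Protocol 8.3), whereas survival is followed much longer: "Information on survival follow-up and new anticancer therapy will be collected every 3 months for up to 2.5 years". A follow-up of that length crosses at least two year-ends.

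At stake are OS, the 12-month OS rate and, within limits, rPFS. All are secondary endpoints, reported to help design later studies.

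**Working it through.** The documents give no figure for this rule, so there is none to reproduce. The dates below are illustrative assumptions. LKA means the last known date alive.

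**Formulas**

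- SAP rule: LKA + 1 day.
- Year-keeping rule, built like the SAP's day-missing bullet: the later of 1 January of the recorded year and LKA + 1 day.

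**1. Contradiction with the record.** LKA is 20 October 2020 and death is recorded only as 2021. The SAP rule gives 21 October 2020. The earliest date the record allows is 1 January 2021: 10 days to the end of October + 30 + 31 + 1 = 72 days later. The latest is 31 December 2021: 72 + 364 = 436 days later. The imputed date is therefore 72 to 436 days too early.

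**2. Where the two rules agree.** With LKA 10 February 2021 and death in 2021, both give 11 February 2021. With LKA 31 December 2020 and death in 2021, both give 1 January 2021. They differ only if the recorded year is later than the year of LKA + 1 day.

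**3. Crossing month 12.** First dose is 28 December 2019, LKA is 10 December 2020 and death is in 2021. The SAP rule gives 11 December 2020, day 349, so the participant counts as dead before 12 months. The year-keeping rule gives 1 January 2021, day 370, so he counts as alive at 12 months. For a simple proportion, one such death moves the estimate by 1/15 = 6.7 points or 1/30 = 3.3 points. For example, 10/15 = 66.7% (Clopper-Pearson 95% CI 38.4% to 88.2%) becomes 9/15 = 60.0% (32.3% to 83.7%).

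**4. rPFS.** SAP 5.4.2.3 counts a death within 16 weeks (112 days) of the last evaluable scan as an event and censors a later one. Take the dates in step 1 and a last scan on 1 September 2020. The imputed 21 October 2020 is 50 days after the scan, so it is an event. The earliest date the record allows, 1 January 2021, is 50 + 72 = 122 days after, so the participant should be censored. This assumes that rPFS uses the same imputed date, that there was no earlier progression, and that no other censoring rule applies.

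**5. How often the year is contradicted.** The documents give no distribution, so assume LKA is uniform over the calendar year and death is uniform from 1 to G days after LKA.

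- Mean shortening under the SAP rule = (G − 1)/2 days.
- Share of year-only deaths placed in the wrong year = (G − 1)/(2 × 365).
- Mean days recovered by the year-keeping rule = (G − 1)(G + 1)/(6 × 365).

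| G (days) | Wrong year | Mean shortening, SAP rule | Recovered | Mean shortening, year-keeping rule |
|---|---|---|---|---|
| 91 | 45/365 = 12% | 45 | 90 × 92/2190 = 3.8 | 41 |
| 105 | 52/365 = 14% | 52 | 104 × 106/2190 = 5.0 | 47 |
| 182 | 90.5/365 = 25% | 90.5 | 181 × 183/2190 = 15.1 | 75 |
| 365 | 182/365 = 50% | 182 | 364 × 366/2190 = 60.8 | 121 |

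A gap of about 91 days matches the three-monthly survival contact. The longer gaps are assumptions for participants whose last contact was further back.

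**The case against.** The case for leaving the rule alone has several parts.

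- **The cases are few.** An affected death needs no fatal AE, a recorded year without a month, and a year-end between LKA + 1 day and the recorded year. A change in the 12-month rate also needs month 12 to fall between the two candidate dates. This stands. The documents give no count, and the number is likely to be small.
- **It changes no decision.** OS is secondary, the SAP plans no hypothesis test or comparison between cohorts, and Stage 2 expansion uses the composite response rate. The error understates survival, so it cannot create an apparent OS benefit. At 15 participants the confidence interval is far wider than one misplaced death. This stands too, and it limits the severity.
- **The repair is only partial.** The year-keeping rule still picks the earliest date the record allows. In the example it recovers 72 days; the rest of the possible 436 remains. This is correct, but the aim is to remove dates the record excludes, not to remove all early-date bias.
- **rPFS is largely shielded.** SAP 5.4.2.3 censors participants who left the study or started other treatment before progression, and those who progressed already have their event. The effect is confined to cases like step 4.

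A reader might also infer that the rule always shortens OS. It does not: if death fell on the day after LKA, the imputed date is exact. A reader might further suppose that the affected deaths are mainly among participants who withdrew or were lost. Protocol 7.2 says only this about records after withdrawal: "However, the study staff may use a public information source (eg, county records) to obtain information about survival status only". Neither document says that such sources give incomplete dates, or in whom partial dates are commonest.

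None of this justifies imputing a date that the participant's own record rules out when the neighbouring bullet already shows how to avoid it.

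**Conclusion.** The point holds in a narrow form. For a death with no fatal AE, a recorded year and no month, the third bullet of SAP 5.6.2 ignores the year. It gives an impossible date whenever that year is later than the year of LKA + 1 day. The rule can never lengthen OS.

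The error is at least 72 days in the worked example. One death moved across month 12 changes a simple proportion by up to 6.7 points at 15 participants or 3.3 at 30. An rPFS censoring can become an event if the false date falls within 16 weeks of the last scan and no other censoring rule applies. The wrong-year shares of 12% to 50% apply to year-only deaths, not to all deaths, and rest on assumed uniform distributions. Severity is minor.

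**What to change.** Split the third bullet of SAP 5.6.2 in two and leave the fatal-AE bullet ahead of both:

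*If the month is missing and the year is known, impute 1 January of the recorded year and take the maximum of that date and the last known date alive plus 1 day. If the year is missing, use the last known date alive plus 1 day.*

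This extends the SAP's own day-missing logic. It costs one sentence in the SAP and one line of code, and needs no new data. A sensitivity run that places affected deaths at the latest date the record allows would show how much early-date bias remains. That run is optional and needed only if such deaths occur.
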